7.4.4 Adverse Drug Events

Adverse drug events (ADE) may be expected to be generally associated with irritation of the nasal mucous membranes in both NONS and placebo treated participants. These events may include headache, pharyngitis, epistaxis, nasal burning/nasal irritation, nausea/vomiting, asthma symptoms, and cough.

7.4.5 Expectedness

An unexpected AE is one of a type not identified in nature, severity or frequency in the current Investigator's brochure. Expected events may include upper respiratory irritation-like symptoms due to use of the nasal spray.

7.5 Adverse Event and Concomitant Mediations Coding

Adverse events will be coded using the current MedDRA dictionary and Concomitant Medications using the current WHODrug dictionary.

7.6 Reporting Serious Adverse Events and COVID-19 Reporting

7.6.1 Serious Adverse Event and Suspected Unexpected Serious Adverse Reaction Reporting

All SAEs that occur from the time of participant enrollment until the end of the study (whether drug related or not) will be documented on an initial SAE form. All SAEs will be reviewed by the Investigator and reported to within 24 hours or specified by regulatory and IRB for SAE reporting.

If only a partial SAE report is available, preliminary information will be documented on an SAE form, reviewed by the Investigator, and reported within 24 hours or specified by regulatory and IRB for SAE reporting. When additional relevant information is available, this information will be submitted on a new SAE form within 24 hours.

Refer to the Safety Management Plan for SAE reporting methods.

Reporting of SAEs to the IRB/IEC will be performed by the Investigator in accordance with the standard operating procedures and policies of the IRB/IEC.

The Sponsor will report SUSARs ([serious adverse drug reactions] that are not identified in nature, severity or frequency in the risk information set out in the Investigator's brochure or on the label of the drug) to the Regulatory Authorities (eg, HC/FDA, or other applicable relevant local/national regulatory authorities) in accordance with regulations (e.g., C.05.014(1)) and related guidance.

7.6.2 Study Sponsor Notification of Adverse Event Outcome by Investigator

Any SAEs, regardless of causality, must be reported to the Sponsor or Sponsor's designee within 24 hours of the Investigator or any staff's knowledge of the event.

Within 24 hours after receipt of additional relevant information, the Investigator must provide Follow-up information on the SAE along with any additional relevant documentation (eg, test results, physician narrative, discharge summary, autopsy findings) that will assist in the understanding of the event.

7.6.3 Institutional Review Board/ Independent Ethics Committee Notification

The Investigator must report all SAEs (including Follow-up information) to the IRB/independent ethics committee (IEC) in accordance with IRB/IEC requirements. Copies of each report and documentation of IRB/IEC notification and receipt will be kept in the local Regulatory files.

7.6.4 Regulatory Reporting Requirements for Serious Adverse Events

- Prompt notification by the Investigator to the Sponsor of a SAE is essential so that legal obligations and ethical responsibilities towards the safety of participants and the safety of a study intervention under clinical investigation are met.
- The Sponsor has a legal responsibility to notify both the local regulatory authority and other regulatory agencies about the safety of a study intervention under clinical investigation. The Sponsor will comply with country-specific regulatory requirements relating to safety reporting to the regulatory authority, Institutional Review Boards (IRB)/IEC, and Investigators.
- For all studies, except those utilizing medical devices Investigator safety reports, must be
 prepared for SUSAR according to local regulatory requirements and Sponsor policy and
 forwarded to Investigators as necessary.
- An Investigator who receives an Investigator safety report, describing a SAE or other specific safety information (e.g., summary or listing of SAEs), from the Sponsor, will review and then file it along with the Investigator's Brochure. He or she will then notify the IRB/IEC, if appropriate according to local requirements.

7.6.5 COVID-19 Health Authority Notification

Health Canada/FDA, and other relevant local/national regulatory authorities must be notified of any participant who contracts COVID-19 during the study (if applicable).

7.7 Treatment-Emergent Adverse Events

Information regarding the occurrence of treatment-emergent AEs (TEAEs) will be captured throughout the study and verified at each telehealth assessment. A description of the AE, duration (start and stop dates and times), severity, outcome, treatment and relation to study medication will be collected.

7.8 Adverse Events of Special Interest

- COVID-19 related symptoms or diagnosis
- Non-compliance for any reason
- Complaints or unanticipated problems associated with the manual pump and spray bottle or use of these, especially malfunction of the manual pump spraying apparatus or a deterioration in its effectiveness, or inadequacy of the directions for use

7.9 Adverse Event, Serious Adverse Event, and Adverse Events of Special Interest Follow-Up

After the initial AE/SAE report, the Investigator is required to proactively follow each participant at subsequent assessments/contacts. All SAEs, and AEs of special interest will be followed until resolution, stabilization, the event is otherwise explained, or the participant is lost to Follow-Up (Section 7.12.3).

7.10 Pregnancy Reporting

Should a female participant or female partner of a male participant become pregnant at any time during the study, the Investigator must notify the Sponsor within 24 hours after learning about the pregnancy. The Sponsor will request Follow-up information regarding the course of the pregnancy and its outcome. Voluntary consent must be obtained from a female participant or female partner of a male participant (and/or legally authorized representative if the participant is mentally incompetent or physically incapacitated) before any pregnancy-related follow-up is obtained.

Pregnancy, in and of itself, is not considered an AE, unless there is suspicion that the study product may have interfered with the effectiveness of a contraceptive medication or method. However, any pregnancy complication or elective termination of a pregnancy for medical reasons will be recorded as an AE or SAE and will be followed accordingly. A spontaneous abortion is considered to be an SAE.

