3.3 Study Duration and Dates

Actual overall study duration or participant recruitment period may vary. The proposed study start is Q4 2021. A participant's time on the study is expected to last 5 weeks from enrollment. Subject participation will consist of 5 days of Screening/Baseline, and 28 days study treatment, followed by 7 days of Follow-Up for safety assessments. Participants should complete the study on Day 35.

For participants that test positive for COVID-19, Health Canada (HC)/FDA, or other applicable relevant local/national regulatory health authorities should be notified as applicable to the regional area. Participants that test positive for COVID-19 will be encouraged to complete early termination assessments and record their symptoms using the COVID-19 symptom list.

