4.2 Inclusion Criteria

Each participant must meet the following criteria to be enrolled in this study.

- 1. At least aged 18 years old at the time of consent.
- 2. If female, be surgically sterile or post-menopausal (no menses for at least 12 months), or if of child-bearing potential, must be using an acceptable method of contraception such as a combination estrogen/progestin hormonal contraceptive (oral or injected) for at least 1 month prior to Day 1, or such items as an intrauterine device (IUD), intrauterine system (IUS), transdermal hormonal implant, vaginal hormonal ring, or two forms of the following: diaphragm, cervical cap, patch, condom, spermicide, or sponge. Total abstinence is permitted. If local regulations deviate from the previously listed contraception methods to prevent pregnancy, local requirements will apply. In addition, females of child-bearing potential must agree to continue to use their method of birth control for the duration of the study and 12 weeks following discharge from the study.
- 3. If male, be surgically sterile, or agree to use appropriate contraception (latex condom with spermicide) when engaging in sexual activity and agree to not donate sperm for the duration of the study and 12 weeks following discharge from the study.
- 4. Be in good health (ie, no acute illnesses or hospitalizations within 30 days of the study start, no planned procedures during study participation, and no newly diagnosed chronic illnesses that are not deemed stable by the participant's primary care physician), in the opinion of the Investigator, based on medical history (ie, absence of any clinically relevant abnormality) during Screening.

- 5. Be able to understand and provide written, informed consent.
- 6. Access to a telephone, the internet, a device that reliability connects to the internet, and able to dial into Telehealth checkups and study related assessments. If access to the internet precludes involvement, then paper diaries may be completed and promptly entered into the data capture system at the study centers as part of the regular follow-up visits.
- 7. Must be able to receive study product shipments directly to their home (ie, no Post Office Boxes), unless in a region (EU) or other location where the participant must receive the study product directly from the sites' staff/physician.

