7 ADVERSE EVENTS ASSESSMENTS

7.1 Adverse Event Definition

As per Good clinical Practice (GCP) guidelines, an AE is any untoward medical occurrence in a patient or clinical investigation participant administered a pharmaceutical product and which does not necessarily have to have a causal relationship with this treatment. An AE can therefore be any unfavorable and unintended sign (including an abnormal laboratory finding), symptom, or disease temporally associated with the use of a medicinal (investigational) product, whether or not related to the medicinal (investigational) product.

AEs will include (1) any new medical condition (sign/symptom/disease) that occurs during the AE reporting period, or (2) any preexisting condition that worsens in severity or frequency or changes in character during the AE reporting period.

An SAE is defined as an AE that, in the view of either the Investigator or Sponsor, meets any of the following criteria:

- Results in death
- Is a life-threatening AE
 - A life-threatening AE is defined as an AE that in the view of either the Investigator or Sponsor, places the patient or participant at immediate risk of death. It does not include an AE that, had it occurred in a more severe form, might have caused death.
- Requires inpatient hospitalization or prolongation of existing hospitalization (except hospitalization for elective procedures for a pre-existing condition that has not worsened, admission to a nursing home or rehabilitation facility, or social admissions)
- Results in persistent or significant disability or incapacity (substantial disruption of the ability to conduct normal life functions; it does not include experiences of relatively minor medical significance such as uncomplicated headache, nausea, vomiting, diarrhea, influenza, or accidental trauma [eg, sprained ankle] that may interfere or prevent everyday life functions but do not constitute a substantial disruption)
- Is a congenital anomaly or birth defect (ie, an adverse outcome in a child or fetus of a female participant exposed to the study product)
- Important medical events that do not meet any of the above criteria may be considered serious when, based upon appropriate medical judgment, they jeopardize the participant and may require intervention to prevent one of the other outcomes listed in this definition

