7.4 Timing

The Sponsor's medical monitor will have read-only access to the AEs recorded within the eCRF. All SAEs must be reported within 24 hours of disclosure/discovery. All SAEs will be recorded and reported to the Sponsor or designee immediately via automatic notification procedures from the eCRF and under no circumstance should this not exceed 24 hours. The Investigator will submit any updated SAE data to the Sponsor within 24 hours of it being available.

Adverse events and SAEs will be collected from the start of study treatment until the Follow-Up assessment as specified in the Schedule of Events (Table 4). Medical occurrences that begin before the start of study intervention but after obtaining informed consent will be recorded on the Medical History/Current Medical Conditions section of eCRF, not on the AE section.

Investigators are not obligated to actively seek AEs or SAEs after conclusion of the study participation. However, if the Investigator learns of any SAE, including a death, at any time after a participant has been discharged from the study, and he/she considers the event to be reasonably related to the study intervention or study participation, the Investigator must promptly notify the Sponsor.

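### Section 7.10 makes a pregnancy notifiable only if it begins during the study, while Section 4.2 requires contraception for 12 more weeks; Section 7.1 also omits a male participant's child from the congenital-anomaly criterion

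*Combined protocol and SAP*

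**What the plan says.** **Contraception (Section 4.2).** Criterion 2 has women of child-bearing potential agree to "continue to use their method of birth control for the duration of the study and 12 weeks following discharge from the study". Criterion 3 has men who are not surgically sterile use contraception and "agree to not donate sperm for the duration of the study and 12 weeks following discharge from the study".

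**Pregnancy reporting (Section 7.10).** The duty arises should a female participant, or a male participant's female partner, "become pregnant at any time during the study, the Investigator must notify the Sponsor within 24 hours after learning about the pregnancy". The Sponsor then asks for the course and outcome. A pregnancy is not in itself an adverse event unless interference with contraception is suspected. Complications and medically indicated terminations are recorded as an AE or SAE, and a spontaneous abortion is an SAE.

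**Length of participation (Section 3.3).** Participation includes "28 days study treatment, followed by 7 days of Follow-Up for safety assessments", and "Participants should complete the study on Day 35". Section 3.3.1 counts a participant as complete at Day 35 or at the early termination assessment. It defines the end of the trial as a whole by the last participant's last assessment.

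**Safety reporting around study end.** Section 7.4 states that "Investigators are not obligated to actively seek AEs or SAEs after conclusion of the study participation", but requires prompt notification of a related SAE learned of at any time after discharge. Section 7.4.1 takes all SAEs, whatever the cause, to 30 days after last dose, and related ones beyond that.

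**Congenital anomaly (Section 7.1).** The SAE criterion is explained as "an adverse outcome in a child or fetus of a female participant exposed to the study product".

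**The concern.** The eligibility criteria ask both sexes to avoid conception for 12 weeks after discharge, yet the pregnancy section attaches no reporting duty to those weeks. A site that follows Section 7.10 exactly has no reason to notify the Sponsor of an uncomplicated pregnancy that begins three weeks after discharge, in a participant or in a partner. The Sponsor would then have no trigger to ask for its outcome.

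The schedule does not make up for this. The last planned contact and urine pregnancy test are at Day 35 or early termination, and Table 4 has no item for a partner's pregnancy or for telling participants to report a later one.

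The second gap concerns men. Criterion 3 restricts them and Section 7.10 follows their partners' pregnancies, but an anomaly in a male participant's child does not meet the congenital-anomaly criterion as Section 7.1 words it.

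At stake is how complete the pregnancy safety information is. Section 9.2 allows up to 11,480 participants to start treatment. A final statement about pregnancies would rest on routine notification over less than a third of the days on which contraception was required.

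**Working it through.** The documents give no figure for pregnancy-reporting coverage, so there is none to reproduce. The check is day arithmetic plus a reading of the SAE rules.

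**Inputs**
- Treatment 28 days and follow-up 7 days (Section 3.3): participation runs to Day 35.
- Post-discharge contraception of 12 weeks (Section 4.2): 12 × 7 = 84 days.
- End-of-study visit window 35 ± 3, i.e. Day 32 to 38 (Table 4).
- Screening of 5 days (Section 3.3) or up to 7 days (Table 4).
- SAE window to 30 days after last dose (Section 7.4.1).

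**Base case, from Day 1**
- Contraception period: 28 + 7 + 84 = 119 days.
- Covered by Section 7.10: 35 / 119 = 29.4%.
- Not covered: 84 / 119 = 70.6%.

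**Range.** Uncovered share = 84 / (pre-treatment days + end-of-study day + 84).
- Highest, no screening days and a visit on Day 32: 84 / (0 + 32 + 84) = 84 / 116 = 72.4%.
- Lowest, 7 screening days and a visit on Day 38: 84 / (7 + 38 + 84) = 84 / 129 = 65.1%.

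**How much the SAE window adds**
- It ends at 28 + 30 = Day 58, which is 58 − 35 = 23 days past Day 35.
- Post-discharge days beyond it: 84 − 23 = 61, i.e. 61 / 84 = 72.6% of the 12 weeks, or 61 / 119 = 51.3% of the whole period.
- This is generous. Section 7.6.1 has SAE documentation run only to the end of the study, and the window takes serious outcomes, not pregnancies as such.

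**What is caught if it begins after discharge**

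| Event | Route | Caught? |
|---|---|---|
| Uncomplicated pregnancy, participant or partner | None; not an AE in itself | No |
| Participant's spontaneous abortion by about Day 58 | SAE, 7.10 and 7.4.1 | Yes |
| Participant's serious outcome after about Day 58, judged related | 7.4 and 7.4.1 | Yes, if the site learns of it |
| The same, judged unrelated | None | No |
| Anomaly in a male participant's child | Outside the 7.1 congenital-anomaly criterion | Only by judgement, as an important medical event |

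**After the fix.** Notification would run to Day 35 + 84 = Day 119, and the uncovered share falls to 0.

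**The case against.** Several points on the other side stand.

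- **The SAE rules catch some outcomes.** A reader might infer that nothing about a post-discharge pregnancy would ever be collected. Sections 7.4, 7.4.1 and 7.10 do not support that, as the table above shows.
- **Pregnancies that begin on study stay reportable.** The 24-hour clock starts when the Investigator learns of the pregnancy, so a conception on study that is discovered later still falls under Section 7.10. For participants who complete treatment, every uncovered day lies at least 7 days after last dose.
- **71% is a share of calendar days.** It is tempting to read it as a share of risk. The protocol never calls the 12 weeks a risk period and does not promise outcome collection in them; that link is inferred from the contraception rule. Section 1.5 describes a localized topical product and reports no systemic toxicity signal as measured by methemoglobin, though that is not reproductive data.
- **Not all 11,480 participants are affected.** Surgically sterile participants and post-menopausal women are exempt from the contraception requirement. The documents give neither the size of the remaining group nor a pregnancy rate.
- **The two periods may differ by design.** Different lengths for contraception and for reporting are not a contradiction in themselves. The protocol gives no reason for the difference, however.
- **Instructions may sit elsewhere.** The consent form, the Manual of Procedures and the Safety Management Plan were not available for this review and could ask participants to report later pregnancies. They would be adding to a protocol duty that stops earlier.

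One objection has less force. If the study in Section 7.10 is read at trial level, early enrollees gain some coverage of the 12 weeks. But Section 4.2 itself separates the duration of the study from the weeks after discharge, coverage would depend on enrolment date, and no contact is scheduled after the end-of-study visit.

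**Conclusion.** The point holds as a limited gap in safety reporting. Routine pregnancy notification covers 35 of the 119 days from Day 1 on which contraception is required. The remaining 84 days (70.6%, range 65.1% to 72.4%) have only the partial SAE routes. What is lost is notification of uncomplicated post-discharge pregnancies and of later outcomes judged unrelated, with weaker coverage of male participants' partners. The Section 7.1 wording is a separate and smaller matter: it affects how an anomaly in a partner's child is classified, and does not stop the Sponsor requesting outcomes of partner pregnancies that begin on study.

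The conclusion assumes the participant-level reading of the study, completion at Day 35 and no further instruction in the operational documents. The number of pregnancies affected cannot be estimated from the documents. The primary efficacy analysis and the sample size are untouched.

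**What to change.** 1. **Section 7.10.** Reconcile it with Section 4.2. Keep the existing on-study window and add: *or within the post-discharge contraception period in Section 4.2*. The existing window should not be replaced by one that starts at first dose. Table 4 allows screening up to 7 days before Day 1 and dosing up to 2 days after baseline, so that change would drop a conception between enrolment and first dose, which the present text plausibly covers.
2. **Exit contact.** At Day 35 or early termination, ask participants to tell the site of any own or partner pregnancy in that period. Outcome is then requested under the voluntary consent already described in Section 7.10.
3. **Section 7.1.** Extend the congenital-anomaly criterion to a child or fetus of the female partner of a male participant.

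The contraception rule is not changed. The cost is wording in two sections, one line in the exit script, passive reporting for 12 weeks and follow-up of some extra pregnancies, with no added visit or test. Because reporting is passive, some pregnancies will still be missed.

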7.11 Concomitant Medication Assessments

Concomitant medication usage for a participant will be recorded for the period starting on Day 1 and continuing throughout the study, including medications administered for management of any AEs as described in Table 4.

Concomitant medications to be recorded include prescription and non-prescription drugs, including vaccines (including all previous SARS-CoV-2 vaccine doses), vitamins, herbal supplements, and recreational drugs.

Non-pharmacologic therapies should be recorded if relevant to a reported AE.

7.12 Safety Follow-Up

Safety Follow Up will be conducted on-site or by the qualified medical provider by telephone, as described in the Schedule of Events (Table 4).

7.12.1 Removal of Participants from the Trial or Study Treatment

The Investigator may withdraw a participant from the study for any of the following reasons:

- A protocol violation occurs,
- A serious or intolerable adverse event occurs,
- A clinically significant change in a laboratory parameter occurs,
- The Sponsor or Investigator terminates the study, or
- The participant requests to be discontinued from the study.

A participant may choose to discontinue study treatment and/or withdraw from the study at any time. Participants who become pregnant during the study are to be withdrawn from study treatment. In the absence of a medical contraindication, every effort should be made by the Investigator to encourage participants who prematurely discontinue treatment to remain in the study as appropriate and, at a minimum, follow the participant for safety data collection.

7.12.1.1 **Discontinuation from Study Drug Treatment**

Participants may discontinue for the following reasons: any study drug related AEs that in the opinion of the Investigator, makes it unsafe for the participant to continue; any study drug related AE that repeats upon re-challenge.

A participant may be discontinued prematurely from study drug treatment for the following reasons:

- AE (including hospitalization for COVID-19/sequalae)
- Withdrawal by participant (specify reason in the eCRF)
- Lost to Follow-up
- Pregnancy

- Physician decision (ie, Investigator decision specify reason in the eCRF)
- Sponsor decision (specify reason in the eCRF)
- Noncompliance with study protocol
- Other (specify reason in the eCRF)

7.12.1.2 **Discontinuation from Study**

A participant may be discontinued prematurely from the study (in its entirety) for the following reasons:

- AE (including hospitalization for COVID-19/sequalae)
- Withdrawal by participant (specify reason in the eCRF)
- Lost to Follow-up
- Death
- Physician decision (ie, Investigator decision specify reason in the eCRF)
- Sponsor decision (specify reason in the eCRF)
- Noncompliance with study protocol
- Other (specify reason in the eCRF)

If a participant is withdrawn because of an adverse experience, the participant will be followed and treated by their health care provider (with documented follow-up) until the abnormal parameter or symptom has resolved or stabilized.

If, for any reason, a participant does not complete the study, the reason will be entered on the eCRF. All participants are free to withdraw from participation at any time, for any reason, specified or unspecified, and without prejudice. The Investigator must record the reason for the early termination and document it in the eCRF.

